7.8.1 Adverse Events

AEs will be coded with the most recent version of the MedDRA. The severity of AEs will be scaled according to Common Terminology Criteria (CTC) AE version 5.

Unless otherwise specified, the analyses of AEs will be descriptive in nature. All analyses of AEs will be based on the number of patients with AEs and not on the number of AEs.

For analysis, multiple AE occurrence data on the eCRF will be collapsed into an AE if all of the following applies:

- All AE attributes are identical (Lowest Level Term [LLT], CTCAE grade, action taken with trial medication, therapy required, seriousness, reason for seriousness, relationship, outcome, AE of special interest)
- The occurrences are time overlapping or time-adjacent (time-adjacency of 2 occurrences is given if the second occurrence started on the same day or on the day after the end of the first occurrence).

For further details on the analysis and presentation of AE data refer to BI standards [\(5\)](#).

The analysis of AEs will be based on the concept of treatment emergent adverse events. That means that all AEs with an onset between first drug intake and last drug intake + REP (42 days) will be assigned to the randomised treatment. All AEs with an onset before first drug intake will be assigned to 'screening' and all AEs with an onset after the residual effect period will be assigned to 'post-treatment' (for listings only). For details on the treatment definition, see [Section 6.1](#).

An overall summary of AEs will be presented; along with the standard categories presented additional categories for action taken and drug relationship with each compound, worst CTCAE grade and infusion related reaction response. The frequency of patients with AEs will be summarised by treatment, highest CTCAE grade, primary SOC and PT. The SOC's will be sorted alphabetically; PT's will be sorted by decreasing frequency (within SOC). Only AEs with a given CTCAE grade will be displayed in tables showing AEs by worst CTCAE grade. AEs with a missing CTCAE grade will not be displayed in these tables; a footnote will explain that these AEs are not included and a separate listing of them will be produced if required. The following tables will be produced for AEs during the on-treatment period:

- Patients with AEs
- Patients with any related AE

- Patients with related xentuzumab/placebo AEs
- Patients with related everolimus AEs
- Patients with related exemestane AEs
- Patients with SAEs

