- Patients with related xentuzumab/placebo SAEs
- Patients with related everolimus SAEs
- Patients with related exemestane SAEs
- Patients with other significant AEs, defined as serious and non-serious AEs that lead to dose reduction or permanent discontinuation of any study medication
- Patients with AEs leading to death (no CTCAE grade required)
- Patients with AEs leading to discontinuation of xentuzumab/placebo
- Patients with AEs leading to discontinuation of everolimus
- Patients with AEs leading to discontinuation of exemestane
- Patients with AEs leading to dose reduction of everolimus
- Patients with AEs leading to dose interruption of xentuzumab/placebo
- Patients with AEs of Special Interest (refer to Section 5.2.6.1 of the CTP)

In addition some AEs are considered to be of particular importance and special search categories (SSC) of groupings of PTs based on Standardised MedDRA Queries (SMQ), BI customised MedDRA Queries (BIcMQ) or MedDRA High Level Terms (HLT) are defined at the project level, the latest version of which will be used. Details of the current version are provided in the Table 7.8.1: 1 below.

SSCs summaries of patients with AEs and related AEs by treatment, highest CTCAE grade, grouped term and PT will be produced. Similar summaries will be produced for the BIcMQ SARS-COV-2-infections.

Table 7.8.1: 1 Overview of Special Search Categories

Grouped term	Groupings
Hepatic impairment	SMQ: Drug related hepatic disorders – comprehensive search
Hyperglycaemia narrow	SMQ: Hyperglycaemia / new onset diabetes mellitus (narrow terms only)
Infusion related reaction	SMQ: Hypersensitivity
Non-infectious pneumonitis	SMQ: Interstitial lung disease (narrow terms only)
Renal insufficiency	SMQ: Acute renal failure, SMQ: Proteinuria, HLT: Glomerulonephritis and nephrotic syndrome
Weight loss	BIcMQ: Weight loss
Neutropenia	SMQ: Haematopoietic leukopenia (narrow terms only)
Stomatitis	BIcMQ: Gastrointestinal mucositis (subsearch1: Stomatitis)

Table 7.8.1: 1 Overview of Special Search Categories (cont.)

Grouped term	Groupings
Asthenia	MedDRA PTs of Asthenia, Fatigue, Lethargy, Malaise, and Decreased activity
Haemorrhage	SMQ: Haemorrhage laboratory terms (narrow terms only), SMQ: Haemorrhage terms (excl. laboratory terms)
Anemia	SMQ: Haematopoietic erythropenia
Thrombocytopenia	SMQ: Haematopoietic thrombocytopenia (narrow terms only)
Thromboembolism	SMQ: Embolic and thrombotic, vessel type unspecified and mixed arterial and venous

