Bradycardia	SMQ: Torsade de pointes/QT prolongation, PT of Bradycardia
Rash	BIcMQ: Skin eruptions (subsearch2: Skin rash potentially related to drug use)

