7.8.3 Vital signs

Only descriptive statistics are planned for this section of the report.

In order to investigate potential bradycardia a shift table of heart rate (<60 bpm, ≥ 60 bpm) at baseline by lowest and last on-treatment heart rate (<60 bpm, ≥ 60 bpm) will be produced. Other suitable summaries may be produced to investigate potential bradycardia.

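### The Thromboembolism category in SAP Table 7.8.1: 1 names only the unspecified/mixed-vessel query, so by that name events coded to a specified vein or artery fall outside its patient count

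*SAP*

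**What the plan says.** SAP Section 7.8.1 singles out certain adverse events as important enough to need pooled categories, built from standard MedDRA queries, sponsor-customised queries or high-level terms. The categories "are defined at the project level, the latest version of which will be used", and Table 7.8.1: 1 sets out the version then current.

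- The Thromboembolism row contains one entry: "SMQ: Embolic and thrombotic, vessel type unspecified and mixed arterial and venous".
- The Bradycardia row reads "SMQ: Torsade de pointes/QT prolongation, PT of Bradycardia".
- The Neutropenia row reads "SMQ: Haematopoietic leukopenia (narrow terms only").

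On reporting, the SAP states: "SSCs summaries of patients with AEs and related AEs by treatment, highest CTCAE grade, grouped term and PT will be produced". For adverse events in general it states: "The frequency of patients with AEs will be summarised by treatment, highest CTCAE grade, primary SOC and PT". The same section says that AE analyses count patients, not events.

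Section 7.8.3 adds a separate heart-rate analysis, which begins: "In order to investigate potential bradycardia a shift table of heart rate", with a cut at 60 bpm. Section 7.8.2 lists neutrophils, lymphocytes and white blood cells as separate laboratory parameters.

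**The concern.** A special search category exists to turn scattered preferred terms into one patient count per arm. A reader who sees a row called Thromboembolism will take it to cover clots and emboli in any vessel. The query in the row is named for the residual case, where the vessel type is not specified or is mixed. A deep vein thrombosis, or an event coded to a named artery, has a specified vessel type and on that reading does not belong to it. The table would then carry the label of the whole concept over a count of part of it.

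What is at stake is the reading of a safety table. A low count in either arm could be taken to mean few thromboembolic events when it means few events of unspecified or mixed vessel type.

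The Bradycardia and Neutropenia rows raise a milder question of the same kind: their labels do not describe what their queries are named for.

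**Working it through.** No arithmetic in the plan bears on this. The check compares each row's label with the name of its query, and then asks what else in the plan would supply the missing count.

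**Step 1. Label against query name (SAP Table 7.8.1: 1).**

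| Row | Scope by query name | Match with label |
|---|---|---|
| Thromboembolism | One query: vessel type unspecified or mixed | Narrower than the label |
| Bradycardia | Torsade/QT query plus the preferred term Bradycardia | The preferred term fits; the query names a different condition |
| Neutropenia | Leukopenia query, narrow terms | Broader than the label |

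**Step 2. Is the Thromboembolism entry shorthand for a wider search?** The rest of the table suggests not. Where several queries are wanted, they are all written out. The Haemorrhage row is "SMQ: Haemorrhage laboratory terms (narrow terms only), SMQ: Haemorrhage terms (excl. laboratory terms"), and Renal insufficiency lists two standard queries and a high-level term. Where scope matters it is stated: the hepatic row specifies the comprehensive search, several rows specify narrow terms, and the Stomatitis and Rash rows name a sub-search. A programmer working from this table would apply the vessel qualifier as written.

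**Step 3. Can the pooled count be recovered from the preferred-term tables?** Suppose a patients in an arm have one thromboembolic preferred term and b have another. The number with at least one of the two lies between max(a, b) and a + b, depending on how many have both. The tables give a and b but not the overlap, and each further term widens the range. The per-arm patient count therefore cannot in general be derived from them.

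**Step 4. Does another planned summary fill the gap?**

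- Thromboembolism: none found in the readable text of SAP Section 7.8. The adverse events of special interest in Protocol Section 5.2.6.1 are hepatic injury and pneumonitis.
- Bradycardia: the preferred term is in the row, Section 7.8.3 gives the heart-rate shift table and allows further summaries, and Section 7.8.4 lists ECG results.
- Neutropenia: Section 7.8.2 reports neutrophils as a parameter of their own.

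Only the Thromboembolism row therefore shows both an apparent omission and no substitute. For the other two, the mismatch is one of naming or breadth.

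**The case against.** The strongest reply has four parts.

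1. **The term lists are not visible.** This stands. That vein- or artery-specific events fall outside the query is inferred from its name. A reader might go further and infer that the Thromboembolism table would be nearly empty. The documents do not support that, because they do not show how many terms the query holds or what share of events it would capture.
2. **The table is a snapshot of a project-level list, and the latest version governs.** This also stands as a fact: the list applied at analysis may differ. But nothing in the SAP commits to changing this row, and the version shown has the mismatch.
3. **Every event still appears by preferred term, and the category tables print preferred terms too.** This stands, and it rules out saying that vessel-specific events are missing from the report. It also means that a QT term under Bradycardia, or a leukopenia term under Neutropenia, can be seen on its own line. It does not supply the pooled patient count (Step 3).
4. **Short labels over broad searches are common in this table.** Infusion related reaction, for example, is the hypersensitivity query, and Renal insufficiency includes proteinuria. This is a fair answer on Bradycardia and Neutropenia, and it reduces them to a labelling point. It does not answer the Thromboembolism row, where the search is narrower than the label.

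A reader might also want to put a number on the patients affected. Neither document gives a thromboembolic incidence for this regimen. Thromboembolism is not among the events that Protocol Section 4.4 reports in more than 20% of patients in trial 1280.4. Protocol Section 1.2.3 says only that such events are less frequent with exemestane than with tamoxifen.

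**Conclusion.** The point holds for the Thromboembolism row. Followed as written, the grouped count would leave out events coded to a specified vein or artery, and no planned summary in the available text gives the number of patients per arm with any thromboembolic event.

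This rests on two assumptions: that the query's content matches its name, and that the list applied at analysis keeps this row unchanged. Some SAP sections are removed from the public copy, so the statement about other summaries covers only what can be read.

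The consequence is limited. Protocol Section 7.3.4 makes the safety analyses descriptive, without hypothesis testing. The primary endpoint, its error rate and the expansion criterion do not depend on these rows. No patient number can be attached to the effect.

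Bradycardia and Neutropenia are secondary. A reader might infer that bradycardia or neutropenia events are missed there too; no such omission is shown. The labels still deserve correction. Section 7.8.3 treats bradycardia as a low heart rate, which is not what the torsade/QT query is named for, and Protocol Section 4.4.4 names neutropenia as a risk in its own right.

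**What to change.** - **Thromboembolism:** add the arterial and venous embolic/thrombotic queries to the row. Report patients per arm for the total and for each sub-query.
- **Project-level list:** make the same change there, since that list governs the analysis, and record the version used.
- **Bradycardia and Neutropenia:** relabel the rows to match their content. For Bradycardia, an alternative is to show QT/torsade as its own category beside the preferred term.

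The work is three table rows and a search-list update, with no new data collection. Protocol Section 1.4 indicates that the primary endpoint analysis has been completed, so if the safety tables already exist this means re-running those categories. The downside for the sponsor is a possibly higher, less favourable thromboembolism count.

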7.8.2 Laboratory data

The analyses of laboratory data will be descriptive in nature and will be based on BI standards (6). The same on-treatment periods as considered for the analysis of AEs will be applied for laboratory values. Patients having at least one post-baseline laboratory value will be displayed in the descriptive analyses.

The focus of the laboratory data analysis will be on the following primary laboratory parameters:

- Alanine aminotransferase (ALT), aspartate aminotransferase (AST), total bilirubin, glucose, creatinine, platelets, cholesterol, triglycerides, neutrophils, lymphocytes, haemoglobin and white blood cells.

Descriptive statistics including baseline, last value on-treatment and change from baseline to last value on-treatment will be produced. CTCAE grades for applicable laboratory parameters will be calculated according to CTCAE version 5. The following outputs will be presented for each of the above parameters:

- Transitions of CTCAE grade from baseline to worst on-treatment laboratory value
- Transitions of CTCAE grade from baseline to last on-treatment laboratory value

Patients with no CTCAE grade due to missing laboratory values will be displayed as 'Missing'. Note with version 5 of the CTCAE grading some of laboratory parameters detailed above (ALT, AST and total bilirubin) can no longer be assigned a grade at baseline. For these parameters, the CTCAE shift tables will be replaced by shift tables of pre-defined categories

based on Upper Limit of Normal (ULN) values. A similar approach will also be adopted for creatinine due the ambiguity of CTCAE grading for grades 2 and 3. The pre-defined categories will follow BI standards (7).

Possible clinically significant abnormal laboratory values are defined as those laboratory values that are of CTCAE Grade ≥ 2 and show an increase from baseline value by at least one CTCAE grade. For those parameters for which no CTCAE has been defined, BI standard definition will be used to determine possible clinical significance. Frequency of patients with possible clinically significant abnormal laboratory values will be provided whenever applicable. If no baseline value is available (or CTCAE grading at baseline cannot be assigned) but the patient has a post-baseline laboratory value of CTCAE Grade ≥ 2 an increase from baseline will be assumed, i.e. the laboratory value considered as possible clinically significant.

Hepatic enzyme elevations (potential Hy's law cases):

The assessment of hepatic enzyme elevations will include frequencies of patients falling into the following categories:

- ALT and/or AST ≥ 3 x ULN with total bilirubin ≥ 1.5 x ULN
- ALT and/or AST ≥ 3 x ULN with total bilirubin ≥ 2 x ULN
- ALT and/or AST ≥ 3 x ULN with total bilirubin ≥ 2 x ULN and alkaline phosphatase ≥ 2 x ULN
- ALT and/or AST ≥ 3 x ULN with total bilirubin ≥ 2 x ULN and alkaline phosphatase < 2 x ULN
- Maximum ALT: ≥ 3 , ≥ 5 , ≥ 10 and ≥ 20 x ULN
- Maximum AST: ≥ 3 , ≥ 5 , ≥ 10 and ≥ 20 x ULN
- Maximum ALT and AST: ≥ 3 , ≥ 5 , ≥ 10 and ≥ 20 x ULN
- Maximum total bilirubin: ≥ 1.5 and ≥ 2 x ULN
- Maximum alkaline phosphatase: ≥ 1.5 and ≥ 2 x ULN

Where applicable for defining the above, events can occur in any order, but must occur within 30 days of each other, with an increase of either ALT or AST being the trigger for evaluations. Along with summaries of the above supportive eDISH plots will also be produced.

7.8.3 Vital signs

Only descriptive statistics are planned for this section of the report.

In order to investigate potential bradycardia a shift table of heart rate (<60 bpm, ≥ 60 bpm) at baseline by lowest and last on-treatment heart rate (<60 bpm, ≥ 60 bpm) will be produced. Other suitable summaries may be produced to investigate potential bradycardia.

7.8.4 Electrocardiogram

Electrocardiogram (ECG) results will only be listed; any clinically significant abnormalities will be recorded as either a concomitant diagnosis or an AE.

7.8.5 Others

Not applicable.

